## 12 STATISTICAL CONSIDERATIONS AND DATA ANALYSES

### 12.1 Sample Size Determination

A sufficient number of healthy adult smokers will be screened to randomize approximately 20 healthy adult smokers, to ensure that 12 complete the entire study assuming a 40% dropout and non-evaluable rate. The highest intra-subject CV calculated from previous studies was 13%.

CCI

[REDACTED]

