**Type and Planned Number of Subjects:**

A sufficient number of subjects will be screened to randomize approximately 20 to ensure a minimum of 12 evaluable subjects complete the entire study.

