## 5 STUDY POPULATION

### 5.1 Type and Planned Number of Subjects

A sufficient number of subjects will be screened to randomize approximately 20 to ensure at least 12 evaluable subjects complete the entire study.

An enrolled subject is one who has agreed to participate in the clinical study following completion of the informed consent process directly or via their legally authorized representative and successfully met eligibility criteria to proceed beyond the screening visit as applicable for the protocol design.

This study can fulfill its objectives only if appropriate subjects are enrolled. The following eligibility criteria are designed to select subjects for whom participation in the study is considered appropriate. All relevant medical and non-medical conditions should be taken into consideration when deciding whether a subject is suitable for this protocol.

Subject eligibility to participate in the clinical study should be reviewed and documented by an appropriate member of the investigator's study team before subjects are included in the study.

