### 5.2 Determination of Sample Size

Twenty (20) healthy adult smokers will be enrolled in the study, to ensure that 12 complete the entire study assuming a 40% dropout and non-evaluable rate. The highest intra-subject CV calculated from previous studies was 13%.

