### 5.3 Randomization and Blinding

### Randomization:

Computer generated randomization schedules will be prepared prior to the start of the study. The schedules will be generated through the statistical analysis system (SAS) software, version 9.4. Block randomization will be used. Subjects will be randomly assigned a 3-digit subject number beginning with 0 with the last two numbers being 01-20.

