### 5.4 Subject Withdrawal and Replacement

A subject may withdraw from the study at any time at his or her own request or may be

This document is confidential.

Version: Draft 0.2, 21-Sep-2021

Controlled Document ID: 2805A.00, Effective Date 29-Jul-2019

Filing requirements: TMF Page 13 of 37

GSK Consumer Healthcare

withdrawn at any time at the discretion of the investigator or sponsor for safety, behavioral reasons, or the inability of the subject to comply with the protocol required schedule of study visits or procedures.

The following circumstances require discontinuation of study product and/or premature subject withdrawal:

- Protocol violation that may impact the subject's safety
- Positive test for COVID-19, conducted during the study, at times deemed necessary by Investigator
- Protocol violation that may interfere with the drug's PK profile, including
  - Any reported or suspected noncompliance of the smoking restriction during post dose PK observation period, e.g., CO > 10 ppm at any time during the 36 post dose period
  - Patch falls off or patch is inadvertently removed by the subject or those removed due to subject decision to discontinue from the study
- Withdrawal of informed consent
- Subject lost to follow-up
- Pregnancy

Version: Draft 0.2, 21-Sep-2021

Controlled Document ID: 2805A.00, Effective Date 29-Jul-2019

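### Do 20 randomized subjects really secure 12 evaluable ones when 40% loss is assumed?

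*Protocol*

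**What the plan says.** Four places give the same target. Protocol 12.1 opens with "A sufficient number of healthy adult smokers will be screened to randomize approximately 20 healthy adult smokers" and gives the purpose as "to ensure that 12 complete the entire study assuming a 40% dropout and non-evaluable rate". SAP 5.2 repeats this: "Twenty (20) healthy adult smokers will be enrolled in the study, to ensure that 12 complete the entire study", again with the 40% assumption attached. The Protocol synopsis says "to ensure a minimum of 12 evaluable subjects complete the entire study", and Protocol 5.1 says "to randomize approximately 20 to ensure at least 12 evaluable subjects complete the entire study". These two omit the 40% condition.

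The highest intra-subject CV from earlier studies is given as 13% (Protocol 12.1, SAP 5.2). The text that follows it in Protocol 12.1 is blacked out.

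SAP 5.3 describes subject numbers "beginning with 0 with the last two numbers being 01-20". SAP 5.4 is headed "Subject Withdrawal and Replacement", but its text deals only with withdrawal. The PK population (Protocol 12.2, SAP 6.2) takes subjects who completed both periods without a major deviation affecting the pharmacokinetics. The bioequivalence criterion (Protocol 12.3.1, SAP 9.7) requires the 90% interval for each of three parameters to lie within 0.8 to 1.25.

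**The concern.** Dividing the target by one minus the loss rate gives the sample size at which the expected number left equals the target. It leaves no margin for chance. A reader who sees 12 called a minimum may think the design protects that number, when under a loss probability of 40% it would be missed in about 4 trials out of 10.

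Nothing visible makes up a shortfall. There is no replacement rule despite the heading of SAP 5.4, and numbering stops at 20. A subject lost in either period leaves the primary analysis. If 12 were needed for adequate power, the study could be less likely to succeed than its sample-size paragraph suggests.

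**Working it through.** **Inputs.** Target 12, loss 40%, about 20 randomized, CV 13% (Protocol 12.1); limits 0.8 to 1.25 and a 90% interval (Protocol 12.3.1). Assumed, because the visible text does not give them: independent losses, true ratios of 0.90, 0.95 and 1.00, and 10 subjects per sequence.

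**1. The plan's own figure.** 12/(1 - 0.40) = 20. It is reproduced exactly, and in reverse 20 × 0.60 = 12.

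**2. Chance of reaching 12 if loss is random.** Let X be the number evaluable, X ~ Binomial(20, 1 - loss).

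| Loss per subject | P(X ≥ 12) |
|---|---|
| 40% | 0.596 |
| 35% | 0.762 |
| 30% | 0.887 |
| 25% | 0.959 |
| 20% | 0.990 |

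At 40% loss, P(X ≤ 11) = 1 - 0.596 = 0.404 and P(X ≤ 9) = 0.128.

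**3. The other reading.** If 40% is a planning ceiling, at most 0.40 × 20 = 8 subjects are lost, at least 12 remain, and the wording holds.

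**4. What a shortfall costs.** Power of the two one-sided 5% tests in a 2×2 crossover, per parameter, with σ_w = √ln(1 + 0.13²) = 0.1295. The standard error of the log ratio is σ_w × √[½(1/n₁ + 1/n₂)], where n₁ and n₂ are the evaluable numbers in the two sequences. There are n₁ + n₂ - 2 degrees of freedom, and power is integrated over the distribution of the residual variance.

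| Assumed true ratio | 12 evaluable (6+6) | 10 evaluable (5+5) | Average, each of 10+10 lost with probability 0.40 | Fall from 12 evaluable |
|---|---|---|---|---|
| 0.90 | 66.62% | 58.45% | 64.24% | 2.38 points |
| 0.95 | 91.48% | 85.14% | 88.34% | 3.14 points |
| 1.00 | 97.68% | 93.69% | 94.78% | 2.90 points |

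The average lets loss fall unevenly between the sequences. If every evaluable number is instead split as evenly as possible, the averages are 65.6%, 89.6% and 95.8%, a fall of about 1 to 2 points. That is too favourable, because random loss does not keep the sequences balanced.

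**5. Validity.** At a true ratio of 0.80 the type I error is 0.050 with 8, 10 or 12 evaluable. A smaller set widens the interval and makes bioequivalence harder to show; it does not make a false conclusion more likely.

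**The case for a change.** The best case for a change is that the sample-size paragraph is what ethics committees and regulators use to judge whether 20 is enough. It should not promise a floor when the target equals the expectation, and at n = 20 the standard deviation of the evaluable count is √(20 × 0.6 × 0.4) ≈ 2.2. Both documents call 40% an assumed rate, not a maximum. The synopsis and Protocol 5.1 drop even that condition. Better wording would be nearly free.

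Part of this stands. In the synopsis and 5.1 the unconditional wording is stronger than the calculation supports, and a careful author would have written that about 12 are expected, or that 12 remain if no more than 8 are lost. But Protocol 12.1 and SAP 5.2, where the sample size is justified, attach the condition, and with it the statement is correct. Dividing by one minus the loss rate is the usual convention, and readers of such paragraphs know what it delivers. No assurance probability is claimed in the visible text, so no stated figure is wrong.

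The Replacement heading in SAP 5.4 and the use of enrolled in SAP 5.2, where the protocol has randomized, are editorial slips. With no replacement procedure described and numbers running to 20, an analyst would use the subjects who were randomized.

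Randomizing more would be a real change: at 40% independent loss, 25 give a 92.2% chance of at least 12, and 27 give 96.6%. That is worth the extra exposure only if something depends on the number 12, and nothing visible does.

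**Conclusion.** The concern is right about the probability but does not call for a change. The inflation from 12 to 20 is exact, and the statement holds under the condition given in Protocol 12.1 and SAP 5.2. The 59.6% figure depends on reading 40% as an independent loss probability for each subject; at 30% loss it is 88.7%, and if 40% is a ceiling the 12 is met.

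Neither the PK analysis set nor the bioequivalence criterion has a minimum number, so falling short triggers no rule and alters no estimate. The cost is an average loss of about 2.4 to 3.1 points of power per parameter from its value at 12 evaluable. This rests on a 13% CV, 10 subjects per sequence, random 40% loss and assumed true ratios of 0.90 to 1.00. Because all three parameters must pass, joint power is no higher than the per-parameter figures. The sponsor's own power statement may lie in the blacked-out text and is not disputed here. Rewording would leave recruitment, the analysis and the conclusion as they are.

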### 12.2 Populations for Analysis

The safety population is defined as all randomized subjects who receive at least one dose of study medication.

The PK population is defined as all randomized subjects who completed both periods, and who had no major protocol deviations concerning pharmacokinetics regardless of patch adhesion score.

The following PK analysis set is defined to address the PK objectives and further PK considerations within this study:

- PK analysis set includes all subjects of the PK population, for which the relevant predose-adjusted PK parameters (at least one AUC or  $C_{max}$ ) can be derived. This

analysis set will be used in PK summaries, the primary analysis, and the secondary analysis.

## 12.3 Statistical Analyses

Additional details of the proposed statistical analysis will be documented in the statistical reporting and analysis plan (SAP), which will be written following finalization of the protocol and prior to study unblinding/analysis (as appropriate). This section is a summary of the planned statistical analyses of the most important endpoints including primary and key secondary endpoints.

SAP creation and statistical analysis will be performed by CCI

Pharmacokinetic variables will be calculated by CCI

All concentration and PK data will be listed. This includes any data for subjects who are not included in the analysis (i.e. subjects withdrawn from the study due to adverse events).

### 12.3.1 Primary Analysis(es)

#### Criteria for assessing bioequivalence (on baseline adjusted data).

The bioequivalence between the test and reference treatments will be concluded if the 90% confidence intervals for the ratio of the means of the primary pharmacokinetic parameters  $AUC_{0-t}$  and  $AUC_{0-inf}$  and  $C_{max}$  of the nicotine profiles lie completely within the range 0.8-1.25.

#### Analysis criteria:

When predose concentrations are greater than the lower limit of quantification (LLOQ), baseline-adjusted nicotine plasma concentrations will be used to determine the following pharmacokinetic parameters using standard noncompartmental techniques: maximum plasma concentration observed ( $C_{max}$ ), area under the plasma concentration versus time curve from time zero to the real time corresponding to the last concentration above LLOQ ( $AUC_{0-t}$ ) and the area under the plasma concentration versus time curve extrapolated to infinity ( $AUC_{0-inf}$ ).

## Pharmacokinetics Analysis

### Variables:

For each study product, the following pharmacokinetic parameters will be estimated:

$AUC_{0-t}$ : Area under the plasma concentration versus time curve from time zero to time t, where t is the time of the last measurable plasma concentration of nicotine, estimated, computed using the linear trapezoidal rule

$AUC_{0-inf}$ : Area under the plasma concentration versus time curve calculated from time zero to infinity.  $AUC_{0-inf} = AUC_{0-t} + C(t)/\lambda_z$  where C(t) is the concentration at the last measurable sampling time point and  $\lambda_z$  is the terminal elimination rate constant)

$C_{max}$ : The highest observed plasma nicotine concentration.

### Analyses

The primary objective will be evaluated based on the following comparison:

The nicotine 21 mg patch manufactured at Alza (Reference) versus the 21 mg patch manufactured at GSKCH Dungarvan (Test), in terms of nicotine  $AUC_{0-t}$ ,  $AUC_{0-inf}$  and  $C_{max}$ .

The statistical analyses will be done based on PK analysis set, (see [section 12.2](#) for definition). Safety population will be used for individual plasma concentration listings and figures.

A linear mixed effects model will be fit to the log-transformed PK variables ( $AUC_{0-t}$ ,  $AUC_{0-inf}$  and  $C_{max}$ ), as the dependent variable, and treatment, and period as fixed effects. Subject nested within sequence will be a random effect. Least squares estimates of treatment effects will be calculated and a 90% confidence interval (CI) for the treatment difference will be computed. The treatment difference and its CI will be exponentiated to obtain the ratio of the geometric means between the test and reference products and its CI.

Bioequivalence between the test and reference treatments (on baseline-adjusted data) will be concluded if the 90% confidence interval for the ratio of the means for each of the PK parameters  $AUC_{0-t}$ ,  $AUC_{0-inf}$ , and  $C_{max}$  of the nicotine profiles lie entirely within the interval 0.8 to 1.25.

The PK parameters ( $AUC_{0-t}$ ,  $AUC_{0-inf}$ , and  $C_{max}$ ) will be summarized for each treatment by descriptive statistics (N, arithmetic mean, standard deviation, geometric mean, coefficient of variation, median, minimum, and maximum). A listing containing individual and summary statistics for each PK parameter will be provided. A similar listing will be provided for log and linear plasma concentrations over time containing individual values and summary statistics for each time point.

Individual plasma concentrations will be listed and summarized descriptively at each time point; the concentration vs. time profile will be graphed by formulation for individual subjects and for the mean on both original and logarithmic scales with Safety population.

#### **Correction for non-zero baseline for the primary analysis.**

The pre-dose nicotine concentration will be estimated using the using the  $\lambda_z$  calculated from the subjects own data as follows:

$$C(t) \text{ adjusted} = C(t) \text{ observed} - C(0) e^{-\lambda_z t}$$

This adjustment will only be applied in cases where the pre-dose value is greater than zero.

#### **12.3.2 Secondary Analysis(es)**

The PK analysis set will be used for the secondary analysis.

For each study product, the following pharmacokinetic parameters will be estimated:

$t_{max}$  time to maximum plasma nicotine concentration;

$t_{1/2}$  apparent elimination half-life;

$\lambda_z$  apparent elimination rate constant for plasma nicotine computed as the slope of the regression line of  $\ln(C(t))$  on time. The regression should generally involve at least 3 consecutive measurable concentrations that decrease over time.

The parameters  $\lambda_z$  and  $t_{1/2}$  and  $t_{max}$  be summarized (mean, median, Q1, Q3, minimum, maximum, standard deviation, and coefficient of variation) for each study treatment. A nonparametric analysis will be performed to compare study treatments using the Wilcoxon Signed Rank Test. Median difference, 95% confidence interval and p-value will also be presented.

Additional PK parameters or statistical analyses may be performed as appropriate.

#### **Adhesion**

A frequency table showing the adhesion score for each patch per assessment timepoint.

Summary statistics (mean, sd, minimum, median and maximum) of duration (days) of patch wear for those that fall off.

### **12.3.3 Safety Analysis(es)**

#### **Criteria for assessing safety:**

Vital signs, physical examination, clinical safety laboratory tests and monitoring of adverse events will be used to assess the safety and tolerability of the study products.

#### **Adverse events:**

The assessment of safety will be based on the frequency and severity of AEs that are emergent after subject randomization, including all application site reactions.

The incidence of treatment-emergent AEs will be tabulated after grouping by preferred term within System Organ Class (SOC). AEs will be summarized as the number and percentage of subjects having any AE, an AE by SOC, and an AE by preferred term within SOC. The subset of AEs suspected of a relationship to study patch application will be summarized similarly. All treatment emergent AEs will also be tabulated by severity. Each AE will be attributed to the patch whose application immediately preceded onset of the AE.

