## 4 STUDY DESIGN

### 4.1 Overall Design

This is a 2-arm, single center, single dose, open-label, randomized, two-sequence, two-period crossover, bioequivalence study in healthy adult smokers that have smoked more than 10 cigarettes per day for 1 year prior to inclusion.

Subjects will be randomly assigned to receive a single-dose of one of the following treatments which will follow a cross-over design:

Treatment A: 21 mg/24h NicoDerm CQ (GSK Dungarvan)-Test

Treatment B: 21 mg/24h NicoDerm CQ (Alza)- Reference

In each treatment period, each subject will be dosed once, i.e., a single NicoDerm patch will be placed under fasted conditions to the upper part of the back for a total duration of 24 hours, and then removed. Blood will be sampled regularly at scheduled times for 36 hours following patch application. The pharmacokinetic profile may be altered when a patch loses its adherence to the skin. Therefore, the adhesion of the patch should be monitored. Adhesion will be assessed five times: immediately after patch application, approximately 6, 12 and 18 hours after application and immediately prior to patch removal.

Carry-over effects will be avoided by a wash-out interval of at least 2 days (but no more than 4 days) from patch removal in the first treatment period to subsequent patch application.

The study will consist of an ambulant screening day within 21 days prior first patch application. Subjects will be confined in the study facility from 48 hours pre dosing and for 36 hours post last dosing; pharmacokinetic (PK) blood samples will be obtained at predose (within 1 hour before dosing), 30 minutes and 1, 2, 3, 4, 5, 6, 8, 10, 12, 14, 16, 18, 20, 24, 25, 26, 27, 28, 30, 32, and 36 hours after administration of the patch.

For each subject the duration of study participation is 27 days of which up to 8 days confined.

Subjects are to abstain from smoking during the confinement period and be subject to random measurements of expired carbon monoxide (CO) to confirm abstinence. The CO levels must be  $\leq 10$  ppm throughout the study.

Procedures must be in place to avoid nicotine cross-contamination i.e. all staff members at the clinical site and the bioanalytical laboratory who are involved in this study must not use any tobacco or nicotine containing products to avoid nicotine cross-contamination.

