## 6.2 Administration

Only subjects enrolled in the study may receive study products and only authorized site staff may supply or administer study products. All study interventions must be stored in a secure, environmentally controlled, and monitored (manual or automated) area in accordance with the labeled storage conditions with access limited to the authorized site staff only.

The patches will be applied according to the instruction provided in the US prescribing information (OTC Drug Facts label & Package Insert).

NicoDerm CQ patch (either Test or Reference patch according to randomization list) will be applied after an overnight fasting period of at least 10 hours, with subjects in a sitting position.

Patches will be applied on morning of study Day 1 of each treatment period. The patch will be applied to a clean and dry skin site on the upper back. The site must be relatively free of hair and free of any tattoos, scarring, or redness and free any conditions which in the opinion of the investigator may impact patch adhesion. Hair at the intended patch site could be clipped but cannot be shaved. To ensure adequate adhesion of the patch, the patch should be pressed down firmly on the skin for at least 10 seconds, making sure all the edges are attached. Staff will wash their hands after application. After application, patches may not be touched. No patch reinforcement or over taping is allowed.

Patches will be removed 24 hours after each application. Staff will wash their hands after patch removal.

The patch that will be applied during Period 2 will not to be applied to the same position as the patch that was applied during Period 1 but on the upper back of the contralateral side of the body.

To standardize the conditions on pharmacokinetic sampling days, all subjects will be required to refrain from lying down (except when required for blood pressure, pulse rate measurements), eating, and drinking beverages excepting water which is allowed from 1 hour post dosing, for the first 4 hours after dosing.

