#### Concomitant medication:

Medications/treatments taken after the first patch administration will be documented as concomitant medication/treatments.

Treatment: Treatment is assigned as the last received treatment, except in the case of pre-dose measurements. Any non-adverse event assessment occurring on the same calendar date as a given patch application before dosing would be attributed to the same treatment given on that

This document is confidential.

Version: Draft 0.2, 21-Sep-2021

Controlled Document ID: 2805A.00, Effective Date 29-Jul-2019

Filing requirements: TMF Page 16 of 37

GSK Consumer Healthcare

calendar day. If no patch was applied on the same calendar day then any measurements predose will not be summarized by treatment. Adverse events will be summarized only by the last received treatment.

Age:

Defend as age at Study day 1 = (Study day 1) visit date - date of birth + 1) / 365.25 and truncated to complete years.

Height:

Height (in cm) = height (in inches) \*2.54

Weight:

Weight (in kg) = weight (in lbs) \* 0.4536

BMI:

BMI  $(kg/m^2)$  = Weight $(kg)/[Height(m)^2]$ 

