#### 10.1 Adverse Events

The assessment of safety will be based on the frequency and severity of AEs that are emergent after subject randomization, including all application site reactions.

Treatment-emergent AEs (TEAEs) and non-TEAEs will be listed by subject and treatment. TEAEs will be defined as any AEs that first occurs on or after the date and time of patch administration. Any AE that first occurs pre-dose but worsens in severity after the first patch administration will also be considered a TEAE. Non-TEAEs are those that occur prior to the first administration of the study medication and resolved prior to patch application or that first occur prior to the first patch administration but do not worsen in severity after patch application. AEs will be captured during the study until study exit. Adverse events will be followed-up until complete resolution, or until the Principal Investigator or Medical Sub-Investigator judges safe to discontinue follow-up.

The incidence of TEAEs will be summarized using the Safety Population. Adverse events will be coded using the MedDRA® dictionary Version 24.0. The incidence of treatment-emergent AEs will be tabulated after grouping by preferred term within System Organ Class (SOC). AEs will be summarized as the number and percentage of subjects having any AE, an AE by SOC, and an AE by preferred term within SOC. The subset of AEs suspected of a relationship to study patch application will be summarized similarly. All treatment emergent AEs will also be tabulated by severity. Each AE will be attributed to the patch whose application immediately preceded onset of the AE.

The relationship of TEAEs will be classified according to the study protocol as not related or related (unlikely related, possibly related, or definitely related) to nicotine. The severity of TEAEs will be classified according to the study protocol as mild, moderate or severe.

Incidence of subjects who experienced TEAEs (frequency and the percentage of subjects) will be presented for each treatment and overall by:

- Overall summary of AEs;
- AEs by SOC
- AEs by SOC and PT;
- TEAE by SOC, PT, and maximum severity;
- AEs by SOC, PT, and relationship to the application site;

This document is confidential.

Version: Draft 0.2, 21-Sep-2021

Controlled Document ID: 2805A.00, Effective Date 29-Jul-2019

GSK Consumer Healthcare

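### Application-site reactions are credited by onset time instead of by side of the back, so a late reaction on the Period 1 side is counted against the Period 2 product

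*Protocol*

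**What the plan says.** Three places set the attribution rule, and all rest on time order alone.

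- Protocol 12.3.3, repeated in SAP 10.1: "Each AE will be attributed to the patch whose application immediately preceded onset of the AE".
- SAP 7.3, under the definition of treatment: "Adverse events will be summarized only by the last received treatment".
- SAP 7.4 and 10.1, for incomplete onset: if the onset date is a patch-application day and the time is missing, the event goes to that day's patch. If day and time are both missing, allocation is case by case.

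Local events fall under the same rule. Protocol 12.3.3 bases the safety assessment on "AEs that are emergent after subject randomization, including all application site reactions", and the safety objective covers local as well as systemic effects of both products. SAP 10.1 also plans a table, by treatment, of events by their relation to the application site.

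On placement, protocol 6.2 puts the second patch "on the upper back of the contralateral side of the body", away from the first position.

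**The concern.** For a systemic event, the last patch applied before onset is a reasonable convention, because nothing else in the data separates the two products. For an application-site event, the side of the back does separate them: each side carries only one product. A rule that ignores the side can credit a skin reaction to a product that never touched that skin. The summaries at stake are the application-site tables by treatment, which are the plan's main evidence on local tolerability of the new-site patch against the current one.

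**Working it through.** The plan gives no figure to reproduce here. The check is a timeline, followed by two short calculations.

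**1. When the rule misfires.** Inputs are the wear time (protocol 6.2: "Patches will be removed 24 hours after each application"), the washout (protocol 4.1: "wash-out interval of at least 2 days (but no more than 4 days) from patch removal"), and the schedule in Table 1-1 (application Day 1, removal Day 2, second application Day 5). AE collection ends at study exit under SAP 10.1, taken here as the last PK sample 36 h after the second application. Under protocol 10.3 it ends 5 days (120 h) after the last administration. Hours are counted from the Period 1 application.

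| Washout | Second application | Study exit (+36 h) | 5-day collection (+120 h) |
|---|---|---|---|
| 48 h | 24 + 48 = 72 | 108 | 192 |
| 72 h (schedule) | 24 + 72 = 96 | 132 | 216 |
| 96 h | 24 + 96 = 120 | 156 | 240 |

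A Period 1-side reaction is credited to the wrong product if its recorded onset falls between the second column and the end of collection. In the schedule that is 96 to 132 h, or 96 to 216 h under the protocol's longer collection.

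**2. Missing time on Day 5.** Day 5 is a patch-application day. A Period 1-side reaction with a Day 5 onset date and no time goes to the Day 5 patch under SAP 7.4 and 10.1, even if it was present before that patch was applied.

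**3. Size for one subject.** AEs are tabulated on the Safety Population, planned at about 20. Misplacing one subject lowers one product's incidence by 1/20 and raises the other's by 1/20, so the difference shifts by 2 × 1/20 = 10 percentage points. This is an upper figure. It assumes that the subject has no other site reaction already counted under the Period 2 product and that about 20 subjects receive each patch.

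**4. Direction.** Let pT and pR be the true site-reaction rates, and let f be the share of Period 1 site reactions whose onset is recorded after the second application. Assume balanced sequences, the same f for both products, and no subject with both a misplaced and a correctly placed reaction. Then:

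- observed T = pT(1 − f/2) + pR·f/2
- observed R = pR(1 − f/2) + pT·f/2
- observed difference = (pT − pR)(1 − f)

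The documents give neither the rates nor f. For illustration, assume pT = 30% and pR = 10%, a true difference of 20 points, with 10 subjects per sequence. The expected number misplaced is 10·f·(pT + pR).

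| f (assumed) | Observed difference | Expected reactions misplaced |
|---|---|---|
| 5% | 19.0 points | 0.2 |
| 10% | 18.0 points | 0.4 |
| 20% | 16.0 points | 0.8 |
| 30% | 14.0 points | 1.2 |

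The error shrinks a difference and does not favour a fixed product.

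**The case against.** The strongest reply is that few events can be affected. The rule uses recorded onset, not the time a reaction is first noticed. AEs are elicited every day, including during washout and on Day 4. Footnote a to Table 1-1 requires the back to be examined before each application, so a reaction visible by then should carry a Period 1 onset and be credited correctly. Apart from a Day 5 onset with missing time, that leaves reactions that begin 48 to 96 h or more after a 24 h patch has come off. All AEs are listed, the investigator assesses causality for each, and the exit examination includes skin, so a reader of the listings could trace a misplaced event if its location is recorded.

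Most of this stands and keeps the point small, but it does not remove it. The back examination in the footnote is not carried into the Day 5 pre-dose procedures in protocol 8.2.7 or into SAP 10.5, both of which describe a brief examination of general appearance, heart and lungs. The full examination that includes skin comes at the end of the study, after both patches. A listing also does not correct a table.

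A reader might infer a further fault: that a Period 1 event which worsens in Period 2 is moved to the wrong product. The documents do not support that. Attribution follows onset, so such an event stays with the Period 1 product. The SAP's only worsening rule concerns the first patch: "Any AE that first occurs pre-dose but worsens in severity after the first patch administration will also be considered a TEAE". The documents do not say whether worsening after the second patch opens a new record. Either answer is a convention.

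**Conclusion.** The point holds for a narrow class: application-site reactions on the Period 1 side whose recorded onset follows the second application, or whose onset is dated Day 5 without a time. For these the stated rule names the wrong product, and no other text overrides it. The possible shift is up to 10 points per misplaced subject with 20 subjects. How often it would happen cannot be judged from the documents.

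Three limits apply. The affected tables are descriptive. With balanced sequences (SAP 5.3 plans block randomization) the effect is dilution, so a reader should not infer a bias towards Test or Reference. The primary PK analysis and the bioequivalence conclusion do not depend on AE attribution. A larger shift per subject, from using the 12 evaluable completers as the denominator, would also be unsupported, because AEs are tabulated on the Safety Population.

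This is a modest correction, worth making before the data are seen. The study is open-label, and moving events between products afterwards would be open to challenge.

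**What to change.** In SAP 7.3, 7.4 and 10.1, and in protocol 12.3.3, state that an application-site AE is attributed to the product worn on the affected side of the back, whatever its onset time and including when the time is missing. Take the side from the AE term, the comment or the skin examination. Keep the onset rule for all other AEs.

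The case report form is not among the documents, so check whether the AE page already captures the side. If it does not, add one entry.

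The SAP is at draft 0.2, so its wording change costs little. A new AE-page entry would mean revising a case report form that SAP section 2 lists as final, and a protocol change needs IRB/EC approval. If only the SAP is changed, record the departure in SAP section 11, which now reports none.
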